The most frequently reported AEs ($\geq 20\%$ of patients), regardless of causality or severity, were nausea (40%); AEs associated with blood glucose increases (39%; including Medical Dictionary for Regulatory Activities [MedDRA] preferred terms [PTs] blood glucose elevated, glucose tolerance impaired, and hyperglycemia); fatigue (26%); diarrhea (26%); and decreased appetite (22%).

AEs considered to be related to rociletinib and reported in $> 5\%$ of patients overall are summarized by system organ class (SOC), PT, and dose level in [Table 3-2](#). The most frequently reported treatment-related AEs ($\geq 20\%$ of patients), regardless of severity, were nausea (28%); increased blood glucose, combined terms as in the previous paragraph (33%), and fatigue (20%).

The majority of AEs have been mild or moderate in severity. Rociletinib selectively inhibits mutant EGFR, and as expected, the syndrome of dose related WT-driven rash and diarrhea has not been observed. All reported events of diarrhea were either Grade 1 or Grade 2.

The most common skin reaction reported in patients treated with EGFR-TKIs is a follicular acneiform eruption. In Study CO-1686-008, rash, irrespective of causality, was reported infrequently (overall 6 patients [4%]) and all events were mild. In Study CO-1686 008, only 1 report of dermatitis acneiform and 1 report of follicular rash have been reported to date.

There have been 2 AEs of pneumonitis and 1 SAE of pneumonitis, all assessed as related to rociletinib by the investigator. Patients recovered after steroid therapy, and patients were not rechallenged with rociletinib.

Electrocardiogram (ECG) Changes

Rociletinib exposure is associated with QT interval corrected for heart rate (QT_c) prolongation. The effect takes several days to develop, and is not seen on Day 1 of therapy. Patients with low baseline resting heart rates appear to be at a higher risk for QT_c prolongation during treatment with rociletinib. Typically, the abnormality is evident by Day 15 of therapy, and the increase remains stable with continued dosing.

Prolonged QT_c is managed effectively by dose reduction.

Table 3-2: Treatment-related Adverse Events Reported in at Least 5% of Patients in Study CO-1686-008

SOC PT	< 900 BID FB (N = 38)	900 BID FB (N = 19)	500 BID HBr (N = 18)	625 BID HBr (N = 17)	750 BID HBr (N = 50)	1000 BID HBr (N = 6)	Overall (N = 148)
Number of Patients with at Least 1 Treatment-related TEAE							

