6.3 Exclusion Criteria

Any of the following criteria will exclude patients from study participation (both Cohort A and B, except where otherwise specified):

1. Documented evidence of an exon 20 insertion activating mutation in the EGFR gene

2. Active second malignancy, i.e. patient known to have potentially fatal cancer present for which he/she may be (but not necessarily) currently receiving treatment
 - Patients with a history of malignancy that has been completely treated, with no evidence of that cancer currently, are permitted to enroll in the trial provided all chemotherapy was completed > 6 months prior and/or bone marrow transplant > 2 years prior
3. Known pre-existing interstitial lung disease
4. **Cohort A only:** Patients with leptomeningeal carcinomatosis are excluded. Other central nervous system (CNS) metastases are only permitted if treated, asymptomatic, and stable (not requiring steroids for at least 4 weeks prior to the start of study treatment). **Cohort B only:** Patients with CNS metastases or leptomeningeal carcinomatosis are excluded.
5. Treatment with prohibited medications (eg, concurrent anticancer therapy including other chemotherapy, radiation, hormonal treatment [except corticosteroids and megestrol acetate], or immunotherapy) ≤ 14 days prior to treatment with CO-1686
6. Patients who are currently receiving treatment with any medications that have the potential to prolong the QT interval and the treatment cannot be either discontinued or switched to a different medication before starting CO-1686
 - see <http://crediblemeds.org/> for a list of QT-prolonging medications (includes all medication under categories of Known, Possible and Conditional risk of Torsades de Pointes)
7. Prior treatment with CO-1686, or other drugs that target T790M-positive mutant EGFR with sparing of WT-EGFR eg, AZD9291, HM61713, TAS-121
8. Any of the following cardiac abnormalities or history:
 - Clinically significant abnormal 12-lead ECG, QT interval corrected using Fridericia's method (QTcF) > 450 msec
 - Inability to measure QT interval on ECG
 - Personal or family history of long QT syndrome
 - Implantable pacemaker or implantable cardioverter defibrillator
 - Resting bradycardia < 55 beats/min
9. Nonstudy-related surgical procedures ≤ 7 days prior to administration of CO-1686. In all cases, the patient must be sufficiently recovered and stable before treatment administration
10. Females who are pregnant or breastfeeding

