7.4 Dose Modifications of Protocol-specified Treatment

No dose escalation beyond the starting dose is allowed in either cohort.

Dose reduction steps are allowed for each patient, with the overall number of dose reduction steps at the investigator's discretion. Dose reduction should be in increments of 125 mg BID

with up to 2 dose reduction steps permitted in both cohorts. Any need for further dose reduction, or adjustment from a twice to 3 times daily (TID) dosing regimen should be discussed with the sponsor before implementing. If a TID regimen is used, the total daily dose should not exceed 1,125 mg (i.e. not more than 375 mg TID).

For Grade 3 or 4 hematologic and non-hematologic toxicities (except for nausea/vomiting, alopecia, QTc prolongation and hyperglycemia), the dose should be initially reduced by 125 mg BID (to 500 mg BID, if the starting dose was 625 mg BID; or to 375 mg BID, if the starting dose was 500 mg BID). Re-escalation of dose after resolution of AEs must be discussed with, and approved by the sponsor.

Once the dose has been reduced, treatment continues at that dose level until the next visit; no dose escalation is possible between visits. If a patient continues to experience toxicity, or if dosing with CO-1686 is interrupted for > 14 consecutive days due to toxicity, treatment should be discontinued unless otherwise agreed between the investigator and the sponsor before reintroduction of study drug.

Management of prolonged QTcF

ECGs will be measured throughout the study as described in the protocol. Readings for QTcF prolongation will be based on the average seen in the ECGs for each time point. Patients are required to have within-normal-range potassium and magnesium at enrollment, and these electrolytes should be maintained within range during CO-1686 treatment, if necessary using supplementation. If QTc prolongation of National Cancer Institute (NCI) Common Terminology Criteria for Adverse Events (CTCAE)¹⁵ version 4.03 Grade 3 are observed, CO-1686 will be held until the event has improved to Grade 1. CO-1686 can then be re-started at a reduced dose upon approval by sponsor. If CTCAE Grade 3 or above QTc prolongation recurs, then CO-1686 will be discontinued unless agreed with the sponsor that additional dose reduction can be evaluated. If QTc prolongation changes of CTCAE Grade 4 are observed at any time, CO-1686 will be discontinued permanently.

Management of hyperglycemia

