Appendix C, Table 3. QTcF Changes on ECG by Acetylator Status

	Overall (N = 635)		
	Slow (n = 300)	Intermediate (n = 259)	Rapid (n = 76)
QTcF Post-baseline \geq 450 msec	198 (66%)	131 (51%)	34 (45%)
QTcF Post-baseline \geq 481 msec	92 (31%)	44 (17%)	7 (9%)
QTcF Post-baseline \geq 501 msec	59 (31%)	22 (9%)	1 (1%)
Two of more within 3 days \geq 501 msec	19 (6%)	10 (4%)	0 (0.0)
QTcF Change from Baseline > 30 msec	246 (82%)	171 (66%)	47 (62%)
QTcF Change from Baseline > 60 msec	141 (47%)	57 (22%)	9 (12%)

Abbreviation: ECG=electrocardiogram.

For those patients ongoing on rociletinib trials, informed consent and testing for NAT2 polymorphism status will be offered and the results will be shared with the treating physician. It will be up to the patient in consultation with the treating physician to decide continued participation in the trial in light of the acetylator status results or whether alternative treatment options should be sought.

Regardless of acetylator status, monitoring should be the same for all patients receiving rociletinib whilst on treatment.

STUDY DESIGN

Treatment Regimen and Duration of Therapy

All patients will sign an informed consent which explains the rationale for closing the CO-1686 clinical development program for NSCLC and the option for ongoing patients to continue

receiving study treatment, should they decide to do so and/or if in the opinion of their treating physician they continue to receive clinical benefit.

Patients may continue to receive CO-1686 if the PI and patient deem it is appropriate for the patient though the availability and suitability of alternative treatment options should be considered by the treating physician and discussed with the patient. CO-1686 will be administered daily on a 28-day cycle. Dosing will be delayed or decreased according to protocol-specified toxicity criteria ([Section 7.4](#)). Each dose should continue to be taken with 8 oz. (240 mL) of water and with a meal or within 30 minutes after a meal two times per day. Tablets should be swallowed whole.

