- Consent withdrawal at the patient's own request or at the request of their legally authorized representative.
- Progression of patient's underlying disease.
 - Post-progression treatment is permitted, at the discretion of the Investigatory and with the approval of the sponsor.
- Intercurrent illness that prevents administration of treatment (Reference [Section 7.7](#))
- Any event, adverse or otherwise, that, in the opinion of the investigator, would pose an unacceptable safety risk to the patient.
- Major noncompliance that may affect patient safety.
- Pregnancy.
- Investigator decision.

In addition, the sponsor may discontinue the trial early for any of the reasons noted in [Section 13.6](#) of the protocol.

The date and reason for cessation of treatment will be documented. Patients with ongoing SAEs will be followed until either resolution or stabilization has been determined.

STUDY PROCEDURES

Schedule of Assessments

The procedures and assessments to be performed are outlined in the Schedule of Assessments presented in [Appendix C, Table 4](#). Procedures are synchronized with administration day of treatment unless indicated. The revised evaluations should commence immediately after the patient is consented, maintaining previous treatment cycle and day sequence.

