Appendix C, Table 4. Schedule of Assessments – Extension Phase

	Prior to beginning Amendment 5 Evaluations	Day 1 of each cycle	End of Treatment (28±7 days after last dose)
Informed consent	X		
Physical Examination including vision check		X	X
Vital Signs ^a and Weight		X	X
Concomitant Medications and Procedures		X	X
Contraceptive Counseling ^b			X
Serum Pregnancy Test ^c			X
Fasting Serum Chemistry ^d		X	X
Hematology ^e		X	X
Adverse Events ^f		X	X
Patient Diary ^g		X	X
CO-1686 Dispensing / Administration		X	
ECG Assessments using central ECG machine ^h		X	X
Tumor Scans ⁱ	To be performed per institutional standard of care or every 8 ± 1 weeks (every 2 cycles); scans are not required at the End of Treatment Visit		
Blood for CYP Evaluation (Optional Sampling) ^j		X	

^a = Vital signs (blood pressure, pulse, and temperature) taken predose on drug administration days.

^b = Patients are to continue using effective contraception for 12 weeks after last dose of CO-1686 and report any pregnancies during this period.

^c = Serum β-hCG to be evaluated by local lab and performed only on women of childbearing potential.

^d = Glucose must be measured following an 8 hour fast (no food or liquid other than water). Hemoglobin A1c will be measured on Day 1 of every other cycle while the patient is on study.

^e = Hematology evaluation should include reticulocytes.

^f = Patients will be monitored for AEs from the time the first dose of CO-1686 is administered through 28 days after the last dose.

^g = Patient diaries should be collected and reviewed for compliance at each visit. No diary will be dispensed at end of treatment.

^h = 12-lead ECG (in triplicate, 10-sec tracings > 2 min apart) prior to dosing up to and including Cycle 12, at a minimum. For patients who are ongoing at this time and for whom QTc has been < 470 ms throughout the study, ECG monitoring may be subsequently taken every 3rd cycle thereafter. ECGs will be performed and interpreted locally for patient care decisions; however, tracings should be submitted to the central laboratory for independent evaluation.

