ⁱ = Tumor scans will no longer be required to be submitted to a central reviewer; Disease progression to continue to be assessed locally by the Investigator. If a patient discontinues treatment before progression or is continuing treatment post progression (approval from Sponsor is required), then the decision to conduct additional scans and the frequency of those scans to monitor disease progression will be the responsibility of the treating physician.

^j = Only 1 sample is needed and may be collected at any visit to enable NAT2 analysis.

Day 1 of Each Cycle

Patients will be instructed to **refrain** from taking their dose of oral CO-1686 at home on the day of their clinic visit (Day 1 of the cycle) because the dose will be taken during the clinic visit. The following procedures will be completed:

- Physical examination
 - Including a vision check as part of a standard physical exam
- Weight

- Vital signs (blood pressure, pulse, and temperature)
- 12-lead ECG (in triplicate, 10-sec tracings > 2 min apart) using central ECG machine prior to dosing, up to and including Cycle 12, at a minimum. For patients who are ongoing at this time and for whom QT has been < 470 ms throughout the study, ECG monitoring may be subsequently taken every 3rd cycle thereafter. ECGs will be performed and interpreted locally for patient care decisions; however, tracings should be submitted to the central lab for independent evaluation.
- Fasting serum chemistry (including fasting glucose). HbA1c will be measured every other cycle (Day 1 of Cycle 3, 5, 7 etc).
- Hematology (including reticulocyte count)
- Concomitant medication and procedures
- AE monitoring
- Collection and review of patient diary and CO-1686 drug return
CO-1686 tablets will be dispensed to the patient; patient diary will be provided to the patient
 - Oral CO-1686 will be administered with a meal, or within 30 minutes after a meal. The patient must also drink at least 8 ounces (240 mL) of water when taking CO-1686. Tablets should be swallowed whole.

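### Appendix C states the condition for spacing out ECGs as QT < 470 ms in one place and QTc < 470 ms in another, and Sections 7.4 and 8.3 disagree on glitazones: two minor wording conflicts in safety instructions

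*Protocol*

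**What the plan says.** **ECG spacing.** Appendix C requires triplicate ECGs at Day 1 of each cycle up to at least Cycle 12, and then allows a lighter schedule on one condition.

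- The Day 1 procedure list allows it for ongoing patients "for whom QT has been < 470 ms throughout the study, ECG monitoring may be subsequently taken every 3rd cycle thereafter".
- Table 4 footnote h allows it for those "for whom QTc has been < 470 ms throughout the study". It does not name the heart-rate correction.

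Elsewhere the protocol works mainly with the Fridericia correction. Exclusion criterion 8 in Section 6.3 uses "method (QTcF) > 450 msec". Section 7.4, under its heading on prolonged QTcF, says "Readings for QTcF prolongation will be based on the average seen in the ECGs for each time point", although the hold, restart and stop rules that follow say QTc.

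**Glitazones.** For hyperglycemia, Section 7.4 names glitazones, with metformin and SGLT2 inhibitors, among the agents expected to work better than sulphonylureas or insulin. If the metformin regimen does not control glucose, it offers pioglitazone or an SGLT-2 inhibitor as add-ons to consider. Section 8.3 puts glitazones in its examples of CYP2C8 inhibitors to be avoided, because potent CYP2C8 inhibition may raise CO-1686 plasma levels. Appendix C keeps the Section 7.4 hyperglycemia and QTc guidance in force during the Extension Phase.

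**The concern.** QT and QTc are different quantities, and the protocol treats them so: Section 11.2.5.5 classifies them separately. CO-1686 is associated with QTc prolongation (Section 3.4.1.1), and the spacing rule decides who moves from an ECG every 28 days to one every 84 days (3 × 28). If a site works from the Day 1 list and reads it literally, a patient whose corrected interval has exceeded 470 ms, and whom footnote h keeps on every-cycle ECGs, could be moved to the lighter schedule.

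The glitazone conflict bears on the same risk. Section 3.4.1.1 links QTc prolongation to exposure, and Section 8.3 warns that this class may raise exposure. A site that adds pioglitazone follows Section 7.4 but goes against Section 8.3.

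**Working it through.** The plan gives no figure to reproduce. The ECG point needs a small conversion; the glitazone point is a comparison of texts.

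**Inputs.** The 470 ms threshold is from Appendix C. The correction is Fridericia, as in Sections 6.3 and 7.4. The heart rates are assumptions, since the documents give none for extension patients.

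**Formula.** QTcF = QT / (60/HR)^(1/3), so QT = QTcF × (60/HR)^(1/3).

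| Heart rate (assumed) | QTcF when QT = 470 ms | QT when QTcF = 470 ms |
|---|---|---|
| 55 | 456.6 | 483.8 |
| 60 | 470.0 | 470.0 |
| 70 | 494.8 | 446.5 |
| 75 | 506.3 | 436.3 |
| 80 | 517.3 | 427.0 |

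**At 70 beats/min.** (60/70)^(1/3) = 0.950. QT 447 ms gives QTcF 470.6 ms, and QT 469 ms gives 493.7 ms. All whole-millisecond QT values from 447 to 469 pass the Day 1 text and fail footnote h read as QTcF.

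**Where a given QTcF passes the literal text.** QT < 470 ms when HR > 60 × (QTcF/470)³.

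- QTcF 481 ms: 60 × (481/470)³ = 64.3 beats/min.
- QTcF 500 ms: 60 × (500/470)³ = 72.2 beats/min.

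**Direction.** The literal text is looser above 60 beats/min and stricter below. Exclusion criterion 8 bars "Resting bradycardia < 55 beats/min", so at entry the stricter range is only 55 to 60. That limit applies at entry and not to later visits.

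**Choice of correction.** SAP Section 11.4 computes both Fridericia and Bazett. At 70 beats/min a QT of 470 ms is 507.7 ms under Bazett and 494.8 ms under Fridericia, so an unnamed correction in footnote h leaves some ambiguity of its own.

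**Glitazones, side by side.** Section 7.4 offers two add-ons. An SGLT-2 inhibitor is compatible with both sections. Pioglitazone is compatible with Section 7.4 only. No exception is written in Section 8.3, and neither section refers to the other.

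**The case against.** **On the ECG rule.** The two sentences are otherwise almost identical, which points to a dropped letter. Appendix C says "The procedures and assessments to be performed are outlined in the Schedule of Assessments presented in" Table 4, and Sections 3.1.1 and 5.1.5 say the new schedule replaces those in Section 9 and applies to all patients. A reader might infer that nothing tells a site which line governs; that goes too far, because Table 4 is the stated schedule and it says QTc. Harm also needs several things together: a patient still on drug after Cycle 12, a past QTcF above 470 ms with raw QT always below it, and a site that prefers the list to the table and takes an optional relaxation. Triplicate ECGs would still be done every third cycle with tracings sent to the central laboratory, and Section 3.4.1.1 says "the increase remains stable with continued dosing". All of this stands and makes the point minor. It does not make the Day 1 sentence correct, because that list too is an instruction to sites.

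**On size.** A reader might infer from Appendix C Table 3 ("QTcF Changes on ECG by Acetylator Status") that a known share of patients is affected. The table does not support that. It pools 635 patients dosed at 500 to 1000 mg BID and counts values at any time after baseline, not extension patients after Cycle 12. One row is also inconsistent: slow acetylators at or above 501 ms are printed as 59 (31%), but 59/300 = 19.7%, and the row above prints 92 (31%), which is right since 92/300 = 30.7%. The percentage is the likelier misprint, but the count cannot be ruled out as the error. The number peaking at 481 to 500 ms is therefore 143 − 82 = 61 if the count is right, or 143 − 115 = 28 if the count should be 92. Likewise, the Grade 3 or greater hyperglycemia counts in Table 1 do not measure pioglitazone use, which comes only after metformin fails and is one of two options.

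**On glitazones.** A reader might infer that Section 7.4 mandates a prohibited drug. It does not. Section 7.4 asks only that the drug be considered, and leaves management to local practice and the physician's judgment. Section 8.3 also speaks of caution and of recommended alternatives, and its concern rests on in vitro work. What remains is conflicting guidance. Nor do the documents settle that glitazones should be removed: Section 7.4 gives a mechanistic reason for them (insulin resistance), and no exposure data with pioglitazone are shown.

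**Conclusion.** Both inconsistencies are in current, operative text, and both are minor. The QT wording is very likely a slip, and Table 4 is the schedule to follow. Read literally, though, the Day 1 text is materially looser at ordinary heart rates, by about 25 ms of QTcF at 70 beats/min (494.8 − 470). That figure rests on the assumed heart rate and on reading footnote h as Fridericia. The glitazone texts conflict without a cross-reference, and a site can satisfy both by choosing an SGLT-2 inhibitor. The number of patients affected by either point cannot be derived from the documents. The primary endpoint, the sample size and the efficacy analyses are untouched.

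**What to change.** 1. **ECG rule.** Change QT to QTc in the Appendix C Day 1 text. Naming QTcF both there and in footnote h is a reasonable further step, since exclusion criterion 8 and the Section 7.4 heading and readings use Fridericia. The cost is that some patients stay on every-cycle ECGs.
2. **Glitazones.** Reconcile Sections 7.4 and 8.3. One way is to name the SGLT-2 inhibitor in Section 7.4 as the preferred add-on with a reference to Section 8.3, and to allow pioglitazone only as a stated exception with added ECG monitoring. Whether to remove glitazones altogether is for the sponsor's medical team. The cost is a narrower second-line choice for glucose control.

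Both changes can go into one clarification letter or the next amendment, at no statistical cost.

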#### LIST OF ABBREVIATIONS

AE Adverse event

CR Complete response

CRF Case report form

CTCAE Common Terminology Criteria for Adverse Events

DCR Disease control rate

DLQI Dermatology Life Quality Index

EORTQLQ-C30 European Organization for Research and Treatment of Cancer Core

Quality of Life Questionnaire

HRQOL Health-related quality of life IRR Independent radiology review

MedDRA Medical Dictionary for Drug Regulatory Activities

NSCLC Non-small cell lung cancer
ORR Objective response rate

OS Overall survival

PD Progressive Disease

PFS Progression-free survival

PK Pharmacokinetics

POPPK Population PK

PR Partial response

PRO Patient Reported Outcome

QOL Quality of life

RECIST Response Evaluation Criteria In Solid Tumors

SAE Serious adverse event SAP Statistical analysis plan

SD Stable disease

SLD Sum of longest diameters

StDev Standard deviation

TEAEs Treatment-emergent adverse events

WHO World Health Organization

